Competency-Based Medical Education (CBME), focused on core competencies, is the current trend in medical education. Entrustable Professional Activities (EPAs) describe clinical tasks that interns are deemed competent to perform independently by the end of each training stage (Fu et al., 2023). EPAs, developed by Dutch medical education scholar Olle ten Cate from 2005 onwards, provide a curricular and assessment framework where supervision levels reflect intern competence and trustworthiness in clinical performance (ten Cate et al., 2015). Different medical professions in Taiwan have begun developing their own EPAs. For occupational therapy, under the facilitation of the Taiwanese Occupational Therapy Association, hospitals have started pilot EPA-based clinical assessments and research dissemination (Fu et al., 2023). In the field of physiological occupational therapy, three EPAs exist for hospital use: performing occupational therapy assessment, performing occupational therapy interventions, and providing health education and counseling.

Therefore, the ultimate goal during clinical internships is for students to acquire core competencies and translate them into workplace competencies. To determine if occupational therapy interns meet these goals, we need to use both Mini-CEX and EPAs. This study aims to examine the impact of using these two tools clinically to assess interns' ability to practice independently and whether correlations exist between subscale scores.

5、 Objectives: This study aims to investigate the effects of combining Mini-CEX and EPAs on evaluating interns' independent practice capability and the correlations between scale sub-items. It is expected that students performing well on EPAs and Mini-CEX will demonstrate better clinical performance and operational skills during internships. We hope EPAs will provide stronger evidence of interns' readiness to independently perform medical tasks.

6、 Methods:

(1) Selection criteria and sample size:

(a) Sample size: 50 subjects at Far Eastern Memorial Hospital; 0 at other centers

(b) Inclusion criteria:

(i) Occupational therapy interns in the physical domain at Far Eastern Memorial Hospital

(ii) Provide informed consent to participate

(c) Exclusion criteria: None

(d) Recruitment: Interns in the physiological domain will be recruited during the 6th week of their internship; assessment will be conducted in the 8th week.

(e) Study design:

This is a cross-sectional study involving physiotherapy interns receiving clinical training.

After obtaining consent at week 6, assessments using EPAs and Mini-CEX will be conducted

during the 8th week in the ward. Each assessment takes about 20 minutes. Results will be analyzed two weeks after submission of instructors' internship grades. Since the occupational therapy department covers physiological and pediatric domains with different clinical instructors, pediatric instructors provide consent forms and explain the study to physiological interns. Participation is voluntary and will not affect internship coursework or rights.

(f) Follow-up or rehabilitation plan:

Subjects will follow routine clinical training; EPA and Mini-CEX are routine tests at week 8.

No additional follow-up or rehabilitation needed.

(g) Outcome measures and statistical analysis:

(i) Clinical performance evaluated by Mini-CEX and EPAs

(ii) Statistic analysis:

Descriptive statistics for demographics; Pearson's correlation to explore relationships between variables; multiple linear regression analyses for predictors of clinical performance including age, gender, average self-study time, prior university experience, parents' occupations, and residence. Significance set at $p < 0.05$.

(h) Questionnaires and data collection:

(i) Demographics collected by semi-structured questionnaire covering age, gender, average self-study time, prior university experience, parents' occupation, and residence.

(ii) Mini-Clinical Evaluation Exercise (Mini-CEX):

Developed by Norcini et al. (1995) and officially translated and authorized for use in Taiwan since 2004 (Chen, 2007), the Mini-CEX assesses clinical diagnostic skills of medical interns using structured forms and immediate feedback. The assessment covers seven core competencies and is scored on a scale from 1 to 9 for each item, where higher scores indicate better clinical performance. This tool has demonstrated good reliability and validity (Holmboe et al., 2003).

(iii) Entrustable Professional Activities (EPAs):

Developed by Olle ten Cate starting in 2005 (ten Cate et al., 2015), EPAs evaluate intern competence according to supervision levels required to perform professional tasks safely. Scores typically range from 1 to 5, with higher values indicating greater independence and readiness to carry out clinical activities autonomously. In Taiwan, EPAs have been progressively developed for various medical specialties, including occupational therapy. Promoted by the Taiwanese Occupational Therapy Association, initial pilot studies have been reported (Fu et al., 2023). This study specifically utilizes EPAs related to occupational therapy assessment tasks in the physiological domain.

(2) Duration and schedule:

Five physiological interns per rotation, three rotations per year (approx. 15 participants/year), with enrollment and data collection planned over four years.

(3) Research personnel, roles, and equipment:

No.	Name	Role	Responsibilities
1	[name]	Principal Investigator	Proposal submission, IRB application, progress monitoring
2	[name]	Co-Investigator	Joint planning, writing, materials preparation, data collection and analysis
3	[name]	Co-Investigator	Joint planning, writing, materials preparation, data collection and analysis
4	[name]	Co-Investigator	Joint planning, writing, materials preparation, data collection and analysis
5	[name]	Co-Investigator	Joint planning, writing, materials preparation, data collection and

			analysis
6	[name]	Co-Investigator	Joint planning, writing, materials preparation, data collection and analysis
7	[name]	Co-Investigator	Joint planning, writing, materials preparation, data collection and analysis

7、 Handling of research materials:

(1) Collection and management during study:

- (a) Paper records will be archived in locked cabinets accessible only to the principal investigator.
- (b) Electronic data will be encrypted and stored on Google Drive, password known only by the principal investigator.

(2) Post-study handling and storage duration:

- (a) Paper records archived securely in locked cabinets for 7 years, access restricted to principal investigator only.
- (b) Electronic data stored encrypted on designated computers, de-identified by replacing names with study codes. Password access limited to the principal investigator; others require PI's permission. Data will be securely destroyed by the principal investigator after 7 years.

8、 Protection of participant rights:

(1) Potential physical, psychological, or social harm and remedies:

- No risks expected as participants only need to complete questionnaires.

(2) Conditions and mechanisms for suspension/termination or withdrawal:

- Participants may withdraw at any time if concerns arise, with assurance that withdrawal will not affect internship rights or coursework.

(3) Participant compensation: None.

9、 Expected outcomes:

(1) This study aims to explore the combined use of Mini-CEX and EPAs for assessing interns' independent functioning and correlations between subscale scores, expecting positive correlation between EPA/Mini-CEX performance and clinical skills. This may confirm intern competency for independent practice.

(2) Research ownership and utilization:

- Results belong to the Rehabilitation Department of Far Eastern Memorial Hospital. Findings may be used by occupational therapy clinical instructors to improve teaching effectiveness.

10、 Funding and budget:

- Internal research grant (Project No.: FEMH-2025-C-091)

Item	Description	Amount (NTD)
Operational expenses	Consumables, supplies, books, and miscellaneous (including study personnel costs, wages, labor insurances, health insurances, and labor pension contributions)	135,000
Management fee	10% of operational expenses	13,500
Total		148,500

11、 Conflict of interest:

- This study is solely an internal initiative for new domain research within the unit, with no external collaborations, commercial involvement, or patent issues.

12、 References:

Fu, C. P., Chiang, F. M., Lee, C. Y., Chi, H. Y., Wu, J. L., Lin, Y. J., Li, M. W., Chen, Y. J., Chang, W. Y., Chang, W. D., Huang, S. M., Liao, W. S., Yang, Y. C., Huang, C. K., Kuo, N. J., Liu, T. H., & Chen, Y. L. (2023). Developing the topics of entrustable professional activities in pediatric

occupational therapy in Taiwan: A pilot study. *Taiwan Journal of Occupational Therapy*, 41(2), 91–110. [https://doi.org/10.6594/tjot.202308_41\(2\).0001](https://doi.org/10.6594/tjot.202308_41(2).0001)

Norcini, J. J., Blank, L. L., Duffy, F. D., & Fortna, G. S. (2003). The mini-CEX: a method for assessing clinical skills. *Ann Intern Med*, 138(6), 476-481. <https://doi.org/10.7326/0003-4819-138-6-200303180-00012>

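### The protocol aims to study the effects of combining Mini-CEX and EPAs, but with neither a comparison condition nor an independent criterion of readiness, the design can only estimate how the two tools' scores are associated

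*Protocol*

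**What the plan says.** The Protocol states the aim in two places. The last background paragraph before section 5 says "This study aims to examine the impact of using these two tools clinically to assess interns' ability to practice independently". Section 5 (Objectives) says "This study aims to investigate the effects of combining Mini-CEX and EPAs on evaluating interns' independent practice capability". In both places the question about correlations is joined on as a further aim; it does not define the first. Section 9(1) is softer: it speaks of exploring combined use, and adds that the result may confirm interns' competence to practise independently.

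The design is in section 6(1)(e): "This is a cross-sectional study involving physiotherapy interns receiving clinical training". (The label for the profession differs from the occupational therapy interns named elsewhere; that is a separate matter.) Consent is obtained in week 6 and both assessments take place in week 8. Section 6(1)(f) adds "EPA and Mini-CEX are routine tests at week 8" and "No additional follow-up or rehabilitation needed".

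Section 6(1)(g) gives the outcome as "Clinical performance evaluated by Mini-CEX and EPAs". The analyses are descriptive statistics, "Pearson's correlation to explore relationships between variables", and a multiple linear regression on age, gender, self-study time, prior university experience, parents' occupations and residence. Section 6(1)(h) lists what is collected: the demographic questionnaire, the Mini-CEX and the EPAs.

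**The concern.** An aim about the effect of combining two tools needs something to set the combination against. That can be a condition in which only one tool was used, or a standard of readiness outside both tools that shows whether the pair does better than either alone. The Protocol describes neither.

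Followed as written, the study will produce correlations between EPA and Mini-CEX scores, and these will be the only results available to report against the first aim. A correlation between two instruments does not show that using both improves the assessment. A high value is as compatible with the second tool adding little as with both measuring readiness well. Section 9(2) foresees that clinical instructors may use the findings, so a conclusion wider than the data could reach practice.

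**Working it through.** The question is whether the aim can be estimated. The Protocol gives no power, effect size or standard deviation behind its sample size, so there is no figure to reproduce. There are two ways to read the aim, and each can be checked against the data to be collected.

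**Inputs from the Protocol**
- Sample size: 50 (section 6(1)(a)).
- Assessment: both tools for every participant, in week 8 (sections 6(1)(e) and (f)). That this happens once is inferred from the cross-sectional design and the single week named.
- Variables collected: Mini-CEX scores, EPA ratings, demographic and background questionnaire (section 6(1)(h)).
- Internship grades: mentioned in section 6(1)(e) only to time the analysis, not as an outcome.

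**Reading 1: combining as an exposure that differs between interns or periods**
- Model: Y = b0 + b1·D, where D = 1 if both tools were used and 0 otherwise.
- All 50 interns have D = 1, so the column for D equals the intercept column.
- The design matrix has rank 1 for 2 parameters. b1 cannot be estimated, and a larger N does not help.

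**Reading 2: combining as a question about measurement, within interns**
- Each intern has a Mini-CEX score M and an EPA rating E. With an outside criterion of readiness C, the gain from adding E to M is R²(C on M and E) − R²(C on M). No second group is needed.
- For standardised scores with corr(C, M) = a, corr(C, E) = b and corr(M, E) = r, R²(C on M and E) = (a² + b² − 2abr)/(1 − r²).
- The study estimates r but not a or b, because C is not collected. The gain is therefore not determined.
- A special case shows what r alone can say. If a = b, the gain is 2a²/(1 + r) − a² = a²(1 − r)/(1 + r). It equals a² at r = 0 and approaches 0 as r approaches 1. In that case a higher correlation between the tools means a smaller gain from using both.
- One of the tools cannot stand in for C. If C = M, then R² is already 1 with M alone and the gain is 0 by construction; the same holds for E.

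**What can be answered: the correlation aim**
- Detectable r = tanh[(z for alpha/2 + z for power)/√(N − 3)], two-sided alpha 0.05 (sidedness is not stated, so this is an assumption).
- 80% power: (1.960 + 0.842)/√47 = 0.409, and tanh(0.409) = 0.387.
- 90% power: (1.960 + 1.282)/√47 = 0.473, and tanh(0.473) = 0.440.

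The planned accrual of 5 × 3 × 4 = 60 interns against a target of 50 has no bearing on this point.

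**The case against.** The strongest reply is that the causal or comparative reading is imposed on loose wording. The Protocol openly calls the study cross-sectional, joins the aim to correlations between sub-items, and in section 9(1) speaks only of exploring combined use. It states no hypothesis that two tools beat one. Its nearest comparative phrase, in section 5, is a hope that EPAs will give stronger evidence of readiness. This stands in part: the Protocol does not claim a benefit of combining, and it should not be accused of doing so. But the correlation aim is written separately from the effect or impact aim in both places, so the first aim is not simply another name for the second. If the wording is only loose, tightening it is the right remedy.

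A second reply is that no separate single-tool group is needed, because every intern has a score on each tool. This is correct. A reader might infer that the design would fail even with an outside criterion, since no intern is assessed without both tools. The documents do not support that: with a criterion, both tools could be compared with either one within interns. The missing criterion is therefore part of this point and not a separate matter.

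A third reply is that the statistical analysis plan may fill the gap. It could define how scores enter the regression, or form a combined score, and the Protocol's silence on those details is not held against it here. It could not supply a comparison condition or a criterion that the Protocol does not plan to collect.

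**Conclusion.** The point holds. The aim about the effects of combining the tools, or the impact of using them, cannot be answered by the design as described. As a between-intern or before/after effect it is not estimable at any N (rank 1 for 2 parameters). As a within-intern question it lacks the independent criterion that it needs.

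This is one of two stated aims. It would go too far to infer that the whole study is uninformative: the correlation aim is estimable, with r of about 0.39 detectable at 80% power and 0.44 at 90% under the assumed two-sided 0.05 level.

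The conclusion rests on two assumptions: that the two assessments take place once, in week 8, and that no measure of readiness is collected beyond those listed. If internship grades or another independent rating were to be used as an outcome, the within-intern question could be reopened, but the Protocol does not say so.

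**What to change.** In the last background paragraph and in section 5, restate the aim as estimating the association between EPA supervision-level ratings and Mini-CEX item scores in occupational therapy interns at week 8. Add one sentence saying that the study does not evaluate whether using both tools improves assessment over either alone.

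Section 9(1) needs its own edit, because it contains neither the effects wording nor the impact wording. Align its phrase about combined use with the restated aim, and remove the statement that the result may confirm interns' competence to practise independently.

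This is a wording amendment. It changes no interns, assessments or data. The cost is a more modest claim.

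### Does a sample size of 50 conflict with a recruitment schedule that adds up to 60 interns?

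*Protocol*

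**What the plan says.** Protocol section 6(1)(a) sets the size at one hospital: "Sample size: 50 subjects at Far Eastern Memorial Hospital; 0 at other centers". Section 6(2) gives the schedule: "Five physiological interns per rotation, three rotations per year (approx. 15 participants/year), with enrollment and data collection planned over four years".

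Three other places bear on how the two relate. The inclusion criteria in section 6(1)(b) require that an intern "Provide informed consent to participate". The study design in section 6(1)(e) adds: "Participation is voluntary and will not affect internship coursework or rights". Section 8(2) allows later exit: "Participants may withdraw at any time if concerns arise".

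The protocol gives no consent rate, dropout allowance, power calculation or rule on closing enrolment at 50. It nowhere states 60 as a target.

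**The concern.** Taken at face value, the schedule yields 60 people and the sample-size line says 50. Section 6(2) calls the yearly 15 participants, and 15 is exactly 5 × 3, so the accrual figure seems to carry no allowance for refusal. With full uptake, 50 would be reached at the end of the tenth of twelve rotations. The investigators would then either stop, leaving two scheduled rotations unused, or go past the stated number.

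The number analysed, and so the precision of the correlations, would depend on which line is followed. Stopping after ten rotations would also give 20 interns from the first rotation of the year against 15 from each of the other two (four years of five, against three years of five).

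**Working it through.** **Inputs.** Five interns per rotation, three rotations per year and four years (section 6(2)); 50 subjects (section 6(1)(a)); significance level 0.05 (section 6(1)(g)). Two-sided testing, 80% power and the correlations 0.40 and 0.50 are assumptions made for illustration; the protocol states none of them. Because it gives no effect size or power, 50 cannot be reproduced from a power formula and can only be compared with the schedule.

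**Schedule against target.**
- Interns passing through in four years: 5 × 3 × 4 = 60.
- In three years: 5 × 3 × 3 = 45, which is short of 50.
- Time to 50 at full uptake: 50/15 = 3.33 years, or 50/5 = 10 rotations. In whole years, that is four.
- Uptake at which 60 interns give 50 participants: 50/60 = 83.3%, a loss of 16.7%.

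**Yield at other assumed uptakes.** 70%: 0.70 × 60 = 42. 80%: 48. 90%: 54. 100%: 60. The stated 50 lies inside this range.

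**What 50 against 60 means for one Pearson correlation (Fisher z).**
- Smallest detectable r = tanh[(1.960 + 0.842)/√(n − 3)]. For n = 50: tanh(2.802/√47) = 0.39. For n = 60: tanh(2.802/√57) = 0.35.
- Power for r = 0.40 = Φ[atanh(0.40) × √(n − 3) − 1.960]. For n = 50: Φ(0.4236 × 6.856 − 1.960) = 83%. For n = 60: Φ(0.4236 × 7.550 − 1.960) = 89%.
- 95% confidence interval for r = 0.50 = tanh[atanh(0.50) ± 1.960/√(n − 3)]. For n = 50: tanh(0.549 ± 0.286) = 0.26 to 0.68. For n = 60: tanh(0.549 ± 0.260) = 0.28 to 0.67.

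The ten extra interns move each confidence limit by 0.02 or less.

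**The case for a change.** The strongest case for a change is that enrolment target and recruitment period belong in the protocol: a later analysis plan cannot decide whether interns in the last two rotations are approached. There are no exclusion criteria, only two weeks separate consent from assessment, and both assessments are routine in week 8. Dropout should therefore be small, and nearly the whole 16.7% gap would have to be refusals, for which no rate is given. The regression lists six predictors, so at one parameter each the difference is 50/6 = 8.3 against 60/6 = 10 interns per predictor. One sentence would settle the matter.

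Part of this stands: the protocol does not say whether 50 is a cap or the number expected after refusals. The rest does not amount to a contradiction.

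- Stopping early and overshooting are the only outcomes if every intern consents, and the protocol makes consent a condition and participation voluntary. The yearly 15 is the product of two headcounts and is marked as approximate; one loosely used noun does not turn it into a forecast of 100% consent.
- The 20/15/15 split needs full consent, exactly five interns every time, a start at the first rotation of a year and a hard stop at 50. The protocol states no such start or stop, and it does not use rotation as an analysis variable.
- The regression is thin for six predictors at either size, so choosing 60 would not change how cautiously it should be read.

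The possible edits gain little. Cutting the schedule to ten rotations would remove the slack, so that a single refusal would put 50 out of reach. Raising the number to 60 enrols more people although no stated figure is missed. Writing in 83% as an expected uptake would only restate 50/60, since nothing in the protocol supports that rate independently.

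**Conclusion.** The arithmetic is right: the schedule implies about 60 interns and the target is 50. It is not an inconsistency that needs correcting. A target of 50 out of about 60 available, over the shortest whole number of years that can reach it, is ordinary accrual slack. If uptake is about 83% or higher, the study as written reaches its stated size within its stated time.

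What remains is a small gap in detail, and investigators can fill it sensibly by analysing every consenting intern enrolled. The consequence is minor either way: a detectable correlation of 0.39 against 0.35, and nearly identical confidence intervals, under the assumed two-sided test and 80% power.

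The conclusion rests on reading the 60 as available interns rather than guaranteed participants, which the consent and withdrawal provisions support. Uptake below 83% would leave the study short of 50 (48 at 80%, 42 at 70%), but that is a recruitment risk and not a conflict between the two sections.

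### Is it a fault that the six-predictor regression in 50 interns is read at p < 0.05 without an exploratory label?

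*Protocol*

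**What the plan says.** Section 6(1)(a) sets the size: "Sample size: 50 subjects at Far Eastern Memorial Hospital; 0 at other centers". Section 6(2) gives the accrual: "three rotations per year (approx. 15 participants/year), with enrollment and data collection planned over four years", so about 15 × 4 = 60 interns could be reached.

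Section 5 gives the aim: "This study aims to investigate the effects of combining Mini-CEX and EPAs on evaluating interns' independent practice capability and the correlations between scale sub-items". Section 9(1) repeats it. Neither section names a background characteristic as a predictor.

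Section 6(1)(g)(i) defines the outcome: "Clinical performance evaluated by Mini-CEX and EPAs". Section 6(1)(g)(ii) then lists descriptive statistics, Pearson correlations, and "multiple linear regression analyses for predictors of clinical performance including age, gender, average self-study time, prior university experience, parents' occupations, and residence". It closes with a single threshold for everything: "Significance set at $p < 0.05". In that section the exploratory wording belongs to the correlations; the regression carries no label of its own.

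Section 9(2) adds: "Findings may be used by occupational therapy clinical instructors to improve teaching effectiveness".

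**The concern.** Six background variables are regressed on each of two assessment tools in 50 people, every coefficient is held to the same 5% level, and no objective asks for the result. Parents' occupations and residence may take several categories, so six coefficients is a minimum. Several tests with modest power are a familiar source of chance findings and of overstated estimates among those that reach significance.

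The stake would be in section 9(2). If instructors acted on a spurious predictor such as gender or residence, or took a non-significant result for self-study time to mean that it does not matter, the regression would mislead them. The missing exploratory label seems to invite that reading.

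**Working it through.** **Inputs from the protocol:** n = 50; six predictors; two outcome tools; threshold 0.05.

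**Assumptions, not in the protocol:** two-sided tests, one coefficient per predictor, independent normal predictors in the power simulations, and the true effect sizes. The protocol gives no effect size, power or formula behind the 50, so it has no figure to reproduce.

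**1. Size needed for significance.** Residual df = 50 − 6 − 1 = 43 and t(0.975; 43) = 2.017. Critical partial r = t/√(t² + df) = 2.017/√(4.067 + 43) = 0.294.

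**2. Power for one predictor (simulation).** The last column is a plain Pearson correlation at n = 50, by Fisher's z.

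| True (partial) r | Power, regression | Mean significant estimate ÷ truth | Power, single correlation |
|---|---|---|---|
| 0.2 | 26–27% | 1.9 | 28% |
| 0.3 | 52–53% | 1.3 | 56% |
| 0.4 | 79% | 1.1 | 83% |

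The noncentral F test with noncentrality f² × (50 − 6) agrees at 26%, 53% and 81%. The common shortcut f² × 50 is a little higher, at 29%, 58% and 85%, because it ignores the information spent on the other five predictors. For a large effect, f² = 0.35 (partial r = √(0.35/1.35) = 0.51), power is 97–98% by the two conventions.

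**3. At least one false predictor when none is real.** Independent tests, one outcome: 1 − 0.95⁶ = 26.5%; simulated, about 25%. Two outcomes, independent: 1 − 0.95¹² = 46.0%; simulated with outcomes correlated 0.3 to 0.7, 44% down to 39%.

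**4. Share of declared predictors that are false.** With one of six real, the five null tests give 5 × 0.05 = 0.25 expected false positives:
- r = 0.2: 0.25/(0.25 + 0.269) = 48%
- r = 0.3: 0.25/(0.25 + 0.519) = 33%
- r = 0.4: 0.25/(0.25 + 0.789) = 24%

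With two real, the four null tests give 0.20, and 0.20/(0.20 + 2 × power) is 27%, 16% and 11%. The range depends on assumptions about which the protocol says nothing.

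**5. What a null result leaves open.** An observed partial r of 0 has a 95% interval of ± tanh(1.96/√(50 − 5 − 3)) = ± 0.29.

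**6. Do these figures contradict the protocol?**
- *Power.* Steps 1, 2 and 5 would count against a stated power or detectable effect. None is stated. The table also shows that the six-predictor model costs only a few points of power against a single correlation. The limit comes from 50 interns, not from the regression.
- *False positives.* Step 3 would count against a claim to control error over the family of tests. None is made, and each test keeps its nominal 5% level.
- *Inference.* Steps 4 and 5 would count against a rule that significance establishes a predictor and non-significance removes one. Section 6(1)(g)(ii) sets a threshold only. It does not say what will be concluded on either side of it, nor that confidence intervals will be left out.
- *Dummy coding.* The chance of a false predictor rises to about 35% per outcome only if the variables expand to 10 coefficients read one by one. With one joint test per variable it stays at 24–28%. The protocol fixes neither the categories nor the way they are read.

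**7. What a change would do.** Adding an exploratory label, intervals, joint tests and adjusted R² keeps the 50 interns, the six predictors and the threshold. The power in step 2 and the roughly 25% in step 3 stay where they are.

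**The case for a change.** The strongest case for the concern is that it targets something the protocol does say, not a gap for a later document to fill. One threshold covers both the correlations that the objective asks for and a regression that it does not ask for. The regression is described plainly as a search for predictors, and the findings may reach instructors. About one chance in four of a false predictor per outcome is not trivial, a true partial correlation of 0.2 would be missed about three times in four, and a few sentences would settle the reading.

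The arithmetic stands, and so does the observation that the regression has no label. Anyone reading the results should treat a lone significant predictor as a lead and a non-significant one as unresolved.

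The step from there to a fault does not stand. A shared 5% threshold does not give the regression the same standing as the objective: with no hypothesis and no place in sections 5 or 9(1), it reads naturally as a side analysis. The sentence on instructors follows a paragraph about the two tools and their subscale correlations and does not mention predictors. Five of the six variables (age, gender, prior university experience, parents' occupations, residence) are not things an instructor can change. The same threshold also governs the correlations: seven Mini-CEX items against one EPA score would give 1 − 0.95⁷ = 30% if all were null and independent. The argument therefore does not single out the regression, and it would fit almost any small observational study.

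**Conclusion.** The concern does not hold. The regression has modest power for small and medium effects (about 26–27% at a partial r of 0.2 and 52–53% at 0.3), close to 80% at 0.4, and about a 25% chance of some false predictor per outcome if none is real. These are properties of 50 observations and six tests at 5%. The protocol makes no claim that they contradict: it states no power, no control of error across tests, no predictor hypothesis, and no rule that p alone names or dismisses a predictor. What could be added is reporting and coding detail that commonly belongs in a statistical analysis plan, and it would change no estimate or error rate.

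The figures assume two-sided tests, one coefficient per variable and the listed effect sizes. The conclusion does not depend on them, because it rests on what the protocol does and does not claim. It would change if the protocol presented the regression as confirmatory or stated a power for it.

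### Does one p < 0.05 threshold, with no main Mini-CEX/EPA correlation named, leave the study's answer open to choice after the results are seen?

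*Protocol*

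**What the plan says.** The study aim, stated just before section 5, includes finding out "whether correlations exist between subscale scores". Section 5 (Objectives) puts it in the plural, as "the correlations between scale sub-items". Section 6(1)(a) gives "Sample size: 50 subjects at Far Eastern Memorial Hospital".

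Section 6(1)(g) lists Mini-CEX and EPAs together as the measure of clinical performance and marks neither as primary. Section 6(1)(g)(ii) then plans "Pearson's correlation to explore relationships between variables", and "multiple linear regression analyses for predictors of clinical performance including age, gender, average self-study time" plus three further background variables, six in all. It ends with "Significance set at $p < 0.05".

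On the instruments, section 6(1)(h)(ii) states: "The assessment covers seven core competencies and is scored on a scale from 1 to 9 for each item". Section 6(1)(h)(iii) states: "This study specifically utilizes EPAs related to occupational therapy assessment tasks in the physiological domain". It does not give the number of EPA scores. No section names a main pair of scores, a total score or a dependent variable for the regressions.

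**The concern.** Part of the aim reads as a yes/no question, but the protocol does not say which correlation answers it. Every correlation and every regression coefficient is judged at the same 0.05. An analyst who looked at seven item correlations and put forward the most striking one would run more than a 5% risk of a false positive answer, and would overstate the strength of the association by reporting the maximum of several noisy estimates. Section 9(1) adds weight to this: it expects a positive correlation and suggests that the result could support the view that interns are ready to practise independently. Exploratory wording, a significance cut-off and a hoped-for conclusion sit uneasily together.

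**Working it through.** The protocol states no family-wise error rate, power or target correlation, so there is no figure of its own to reproduce.

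**Inputs from the protocol:** n = 50 (section 6(1)(a)); 0.05 per test (6(1)(g)(ii)); seven Mini-CEX items scored 1 to 9 (6(1)(h)(ii)); EPA scored 1 to 5 (6(1)(h)(iii)); six named predictors (6(1)(g)(ii)).

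**Assumptions:** two-sided tests, one EPA score, multivariate normal data, and equal inter-item correlation over the ranges shown.

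**Step 1. Threshold for one correlation.** With t = 2.0106 on 48 degrees of freedom, r = t/√(n − 2 + t²) = 2.0106/√(48 + 4.0425) = 0.279.

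**Step 2. At least one false positive among seven when nothing is related.** For independent tests, 1 − 0.95⁷ = 0.302. Simulated with correlated items (20,000 replicates):

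| Inter-item correlation | 0.3 | 0.5 | 0.7 | 0.9 |
|---|---|---|---|---|
| At least one of seven significant | 26.8% | 23.2% | 17.7% | 11.2% |

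One correlation named beforehand gives 5%. The expected number of false positives is 7 × 0.05 = 0.35 at any inter-item correlation.

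**Step 3. Mean of the largest of seven when all are equally related** (40,000 replicates):

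| True r | One pre-named item | Inter-item 0.5 | 0.7 | 0.9 |
|---|---|---|---|---|
| 0.3 | 0.297 | 0.424 | 0.397 | 0.355 |
| 0.5 | 0.496 | 0.606 | 0.584 | 0.549 |

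The excess over a pre-named item is 0.355 − 0.297 = 0.058 to 0.424 − 0.297 = 0.127 at a true 0.3, and 0.549 − 0.496 = 0.053 to 0.606 − 0.496 = 0.110 at a true 0.5. With scores rounded to whole points (assumed item mean 6 and SD 1; EPA levels in shares of 2/23/50/23/2%; 10,000 replicates), the largest averages 0.40, 0.38 and 0.34 at a latent 0.3, against 0.26 to 0.27 for one item. At a latent 0.5 it averages 0.56, 0.54 and 0.51, against 0.44. The absolute values fall and the excess remains.

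**Step 4. What the plan itself produces.** Steps 2 and 3 describe reporting one correlation chosen from seven. The protocol contains no such step; it asks for the set. An item's estimate and interval do not depend on which other item carries the label primary. For an observed 0.3, the Fisher-z 95% interval is tanh(0.3095 ± 1.96/√47) = tanh(0.0236) to tanh(0.5954), or 0.02 to 0.53, with or without that label. With all seven shown, a reader can set one significant result against the 0.35 expected by chance.

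**Step 5. What a named primary would buy.** Its error rate would be 5%, with 80% power at r = tanh((1.960 + 0.842)/√47) = 0.387. Keeping all seven as confirmatory tests with a Bonferroni level of 0.05/7 = 0.00714 would raise the detectable r to 0.474. A natural primary, the mean of the seven items against the EPA level, answers an overall question rather than the sub-item question in section 5.

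**Step 6. Regressions.** Six independent null predictors give 1 − 0.95⁶ = 0.265. No stated objective depends on these models, so this adds nothing to the question about correlations.

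**The case for a change.** The best argument for a change is that identifying the main result belongs in a protocol. A wholly exploratory study needs no significance cut-off, yet this one sets a cut-off, predicts a direction and hopes to support a conclusion about competence. One paragraph would remove the ambiguity and would need no new data.

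Part of this stands. No main association is named, section 9(1) is worded more firmly than section 6(1)(g)(ii), and anyone who did report only the largest correlation would mislead readers by the amounts shown.

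The rest does not carry. The analysis sentence itself describes the correlations as exploration. The hoped-for conclusion in section 9(1) concerns interns' competence, not any single item correlation. A 0.05 level per test is not wrong in itself, and nothing in the protocol conflicts with reporting every correlation. Which score leads, how it is formed and which results are labelled exploratory are commonly settled in a statistical analysis plan, and that document is not at hand. Making a composite score primary in a small study whose stated interest is the sub-items is a fair preference, but it corrects no error.

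**Conclusion.** No change to the protocol follows. It is silent on a main association, but it makes no false or contradictory statement on the point. Following it as written, with the full set of sub-item correlations reported, gives a sound exploratory result.

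The risk arises only if one correlation is selected afterwards. It would then be about 11% to 23% against 5% under a complete null, and an average of about 0.35 to 0.42 reported for a true 0.3. These ranges assume n = 50, one EPA score, normal data and inter-item correlations of 0.5 to 0.9, none of which except n is in the protocol. More EPA scores would raise the figures. The complete null is also the worst case: both tools rate the same intern in the same week, so some true association is plausible, and a positive answer would then not be false. The conclusion rests on the analysts reporting all the correlations, which is what section 5 asks for.
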